7.1.3 Secondary Variables

7.1.3.1 SKAMP

The onset of efficacy, based on the SKAMP total scores, will be defined as the time of the first assessment time showing statistical significance between d-ATS and placebo. If no significant difference is found at any time point for the onset of efficacy, no onset of efficacy will be deemed to have occurred, and the onset of efficacy will be defined as 'none'.

Onset of efficacy as measured by the SKAMP total score (defined in Section 5) will be analyzed using the same MMRM model as for the primary analysis. In the model, the SKAMP total scores for each timepoint will be analyzed with the fixed effects of sequence (two levels), period (two levels), treatment (two levels) and time (10 levels, one for each of 30 minutes prior and 1, 2, 3, 4.5, 6, 7, 9, 10, and 12 hours post dosing) while the repeated effect will be defined for subject-within-sequence. The interaction term for treatment * time will be included in the model, but not tested for significance. The example SAS code shown in section 7.1.1 may be used for this analysis, substituting the estimate statement given (mean estimates across timepoints) for the following set of statements (mean estimates at each timepoint):

```
estimate 'd-ATS - Placebo 1hr post dose'  
<treatment> -1 1  
<treatment*timepoint> 0 -1 0 0 0 0 0 0 0 0 0 0 0 0 0 0 0 0 0 0 0  
/ cl;  
  
estimate 'd-ATS - Placebo 2hrs post dose'  
<treatment> -1 1  
<treatment*timepoint> 0 0 -1 0 0 0 0 0 0 0 0 0 0 0 0 0 0 0 0 0 0  
/ cl;  
  
estimate 'd-ATS - Placebo 3hrs post dose'  
<treatment> -1 1  
<treatment*timepoint> 0 0 0 -1 0 0 0 0 0 0 0 0 0 0 0 0 0 1 0 0 0 0 0  
/ cl;  
  
estimate 'd-ATS - Placebo 4.5hrs post dose'  
<treatment> -1 1  
<treatment*timepoint> 0 0 0 0 -1 0 0 0 0 0 0 0 0 0 0 0 0 0 1 0 0 0 0  
/ cl;  
  
estimate 'd-ATS - Placebo 6hrs post dose'  
<treatment> -1 1  
<treatment*timepoint> 0 0 0 0 0 -1 0 0 0 0 0 0 0 0 0 0 0 0 0 1 0 0 0  
/ cl;  
  
estimate 'd-ATS - Placebo 7hrs post dose'  
<treatment> -1 1  
<treatment*timepoint> 0 0 0 0 0 0 -1 0 0 0 0 0 0 0 0 0 0 0 0 0 1 0 0 0
```

```
estimate 'd-ATS - Placebo 9hrs post dose'  
<treatment> -1 1  
<treatment*timepoint> 0 0 0 0 0 0 0 -1 0 0 0 0 0 0 0 0 0 1 0 0  
/ cl;  
  
estimate 'd-ATS - Placebo 10hrs post dose'  
<treatment> -1 1  
<treatment*timepoint> 0 0 0 0 0 0 0 0 -1 0 0 0 0 0 0 0 0 0 1 0  
/ cl;  
  
estimate 'd-ATS - Placebo 12hrs post dose'  
<treatment> -1 1  
<treatment*timepoint> 0 0 0 0 0 0 0 0 0 -1 0 0 0 0 0 0 0 0 0 0 1  
/ cl;
```

The two treatment levels will be: d-ATS (5, 10, 15, 20 mg doses combined) and placebo. Continuous summary statistics will be presented for the SKAMP total score at each time point for Visits 6 and 7 for the FAS population. Raw means, LS means, differences in LS means, and 95% CI for the difference between treatment arms, and p-values will be calculated for each post-dose time point and for mean score over the treatment day for the FAS population.

The SKAMP total scores will also be plotted by time point for the FAS population.

Scaled residual and random effects plots will be considered to check the assumptions behind the mixed model.

The assessment of treatment differences will follow the closed testing procedure described in Section 7. The closed testing procedure starts from the time-point of 1 hour post-morning dose, then 2, 3, 4.5, 6, 7, 9, 10 and 12 hours post-dose. At each timepoint the order of testing will be onset of efficacy followed by duration of efficacy, before moving to the next timepoint. Duration of efficacy will not be considered until onset of efficacy has been determined.

- The onset time of efficacy action will be determined as the first post-dose time where the difference between the two treatments is statistically significant (i.e., $p \leq 0.05$).
- If the difference between the two treatments is statistically significant (i.e., $p \leq 0.05$) at the 1 hours post-dose time point, the duration of efficacy will be claimed as the difference in hours between the end of efficacy; the last consecutive time point at which the difference is still statistically significant (i.e., $p \leq 0.05$) and onset of efficacy. If there is no time point at which there is a non-significant difference between the two treatment groups after a time point in which there is a significant difference between the two treatment groups, then the end of efficacy will be defined as 12 hours post-dose.

For example, if a statistically significant difference in mean SKAMP total scores for d-ATS vs. placebo was determined at 1 hour post-dose and statistical significance was measured at all time-points up to and including 10 hours post-dose, but statistical significance was not reached at 12 hours post-dose, onset of clinical efficacy and end of clinical efficacy would be defined as 1 hours post-dose and 10 hours post-dose, respectively, with duration of efficacy being 9 hours.

Supportive analysis of onset of efficacy and duration of efficacy will be conducted using the same model for the Completers population.

Onset and duration of effect as measured by the SKAMP total score (defined in Section 5) will be analyzed using two methods, firstly an MMRM model approach will be considered for the analysis of Onset and Duration of efficacy. Secondly a summary measures and survival analysis approach for onset and duration of effect for 50% reduction in SKAMP total score will be conducted.

Onset of effect for 50% reduction in SKAMP total score is defined for each subject as the first time point at which there is a 50% reduction in SKAMP total score from the pre-dose observation on the same classroom day.

Continuous summary statistics will be presented for the SKAMP total score at each time point for Visits 6 and 7, for the time of effect onset and for the duration of effect (hours) for the FAS.

Time of onset of effect for 50% reduction in SKAMP total score will be summarized descriptively and displayed graphically using the Kaplan-Meier approach for the FAS. The upper and lower quartiles (and CI) as well as the 50th percentile (and CI) will be used to estimate median time of onset of effect in each treatment arm. The difference between treatment arms, d-ATS and placebo, will be assessed using the Log-Rank test. Subjects that do not record a 50% reduction in SKAMP total score from the baseline value will be deemed to be censored at the last timepoint a SKAMP total score is recorded, for each classroom day.

Duration of effect for 50% reduction in SKAMP total score will be determined by persistence of the reduction of 50% from the pre-dose observation in SKAMP total score. The end of effect will be determined as the first timepoint after onset of effect at which the 50% reduction in SKAMP total score is not observed. The duration of effect will be calculated as the difference between the end of effect and onset of effect, in hours. Duration of effect will be analyzed using the same methodology as the onset of effect. Subjects that record a 50% reduction in the SKAMP total score from the baseline value such that duration of effect continues at their final assessment time for that classroom day will be censored at that time. Subjects without an onset of effect will be excluded from the analysis of duration of effect. A sensitivity analysis will be performed where subjects without an onset of effect will be imputed to have duration of effect of 0 hours.

Supportive analysis of onset of efficacy and duration of efficacy will be conducted using the same approach for the Completers population.

Once onset and duration of efficacy are estimated (using the MMRM approach analysis for the FAS, as described above), the sensitivity analysis will be conducted for primary variable as specified in section 7.1.1 by excluding data from time points before onset and after the last time point included into the duration of efficacy.

All data, including derived values, will be listed.

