### 8.2.2 Secondary Efficacy Analysis

The onset of efficacy, based on the SKAMP total scores, will be defined as the time of the first assessment time showing statistical significance between d-ATS and placebo. If no significant difference is found at any time point for the onset of efficacy, no onset of efficacy will be deemed to have occurred, and the onset of efficacy will be defined as 'none'. Onset of efficacy as measured by the SKAMP total score will be analyzed using the same MMRM model as for the primary analysis.

To preserve the Type I error rate in analyzing these endpoints of onset and duration of efficacy, a closed test procedure will be used. The closed test principle states that the trial-wise error rate can be controlled by the ordered testing of each hypothesis in the closed family using a suitable  $\alpha$  level significance. A condition of the Closed Test procedure is that the order of testing of the endpoints in a family matters. Thus hypotheses in a family must be ordered and the testing of each subsequent hypothesis in the order can only proceed if the testing of the prior hypothesis achieves a significant p-value with Type I error rate of predetermined  $\alpha$  level, which will be set at  $\alpha = 0.05$  for this study. Testing of the hypotheses in the family proceeds until a hypothesis fails to achieve a significant p-value. If/when a hypothesis in the family fails to achieve significance, then significant p-values cannot be claimed for all subsequent hypotheses in that family, i.e., once one hypothesis fails to achieve significance, testing should cease.

If the primary efficacy endpoint, difference between d-ATS and placebo in mean SKAMP total score for the double-blind phase, is statistically significant (i.e.,  $p < 0.05$ ), the secondary variables of onset and duration of efficacy will be tested using a closed testing procedure. The closed testing procedure starts from the time-point of 1 hour post-morning dose, then 2, 3, 4.5, 6, 7, 9, 10 and 12 hours post-dose. At each timepoint the order of testing will be onset of efficacy followed by duration of efficacy, before moving to the next timepoint. Duration of efficacy will not be considered until onset of efficacy has been determined.

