5. DEFINITIONS

SKAMP Total Score

The SKAMP total score will be the sum of the 13 individual item scores at each timepoint. Missing data will not be handled at an item level, if any of the 13 items are missing for a timepoint then the SKAMP total score will be missing for that timepoint.

Mean SKAMP Total Score

The mean SKAMP total score will be the average of all SKAMP total scores collected over the course of a laboratory assessment day, with the exception of the score from the session prior to dosing.

Onset of efficacy

The onset of efficacy, based on the SKAMP total scores, will be defined as the time of the first assessment time showing statistical significance between d-ATS and placebo. If no significant difference is found at any time point for the onset of efficacy, no onset of efficacy will be deemed to have occurred, and the onset of efficacy will be defined as 'none'.

Duration of efficacy

The duration of efficacy, based on the SKAMP total scores, will be defined as the difference between the time point that indicates that the effect has ended and the onset of efficacy, as defined above. The time point that indicates that the effect has ended will be defined as the first time point at which there is a non-significant difference between the two treatment groups after a time point in which there is a significant difference between the two treatment groups. If there is no time point at which there is a non-significant difference between the two treatment groups after a time point in which there is a significant difference between the two treatment groups, then the end of effect will be defined as 12 hours post-dose.

Onset of effect (50% reduction in SKAMP total score)

Onset of effect of 50% reduction in SKAMP total score is defined for each subject as the first time point at which there is a 50% reduction in SKAMP total score from the pre-dose observation on the same classroom day.

Duration of effect (50% reduction in SKAMP total score)

Duration of effect of 50% reduction in SKAMP total score will be determined by persistence of the 50% reduction from the pre-dose observation in SKAMP total score level. The end of effect will be determined as the first timepoint after onset of effect at which 50% reduction from the pre-dose observation in SKAMP total score is not observed. The duration of effect will be calculated as the difference between the end of effect and onset of effect, in hours.

Age

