To preserve the Type I error rate in analyzing the secondary endpoints of onset and duration of efficacy, a closed test procedure will be used. The closed test principle states that the trial-wise error rate can be controlled by the ordered testing of each hypothesis in the closed family using a suitable α level significance. A condition of the Closed Test procedure is that the order of testing

of the endpoints in a family matters. Thus hypotheses in a family must be ordered and the testing of each subsequent hypothesis in the order can only proceed if the testing of the prior hypothesis achieves a significant p-value with Type I error rate of predetermined α level, which will be set at $\alpha= 0.05$ for this study. Testing of the hypotheses in the family proceeds until a hypothesis fails to achieve a significant p-value. If/when a hypothesis in the family fails to achieve significance, then significant p-values cannot be claimed for all subsequent hypotheses in that family, i.e., once one hypothesis fails to achieve significance, testing should cease.

If the primary efficacy endpoint, difference between d-ATS and placebo in mean SKAMP total score for the double-blind phase, is statistically significant (i.e., $p<0.05$), the secondary variables of onset and duration of efficacy will be tested using a closed testing procedure. The closed testing procedure starts from the time-point of 1 hour post-morning dose, then 2, 3, 4.5, 6, 7, 9, 10 and 12 hours post-dose. At each timepoint the order of testing will be onset of efficacy followed by duration of efficacy, before moving to the next timepoint. Duration of efficacy will not be considered until onset of efficacy has been determined.

All data collected will be presented in data listings, and the listings will be sorted by investigator/site, subject, and time point.

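### The gate, onset and end-of-effect rules ask for a significant difference but never one that favours d-ATS, so a late reversal would lengthen the claimed duration

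*SAP*

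**What the plan says.** Three rules decide whether and for how long efficacy is claimed on the MMRM analysis.

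- **Gate.** Onset and duration are tested only when the primary comparison succeeds, which SAP 7 states as the "difference between d-ATS and placebo in mean SKAMP total score for the double-blind phase, is statistically significant", with p below 0.05. Protocol 8.2.2 has the same condition.
- **Onset.** SAP 7.1.3.1: "The onset time of efficacy action will be determined as the first post-dose time where the difference between the two treatments is statistically significant", with p at or below 0.05. SAP 5 and protocol 8.2.2 agree: "the first assessment time showing statistical significance between d-ATS and placebo".
- **End of effect.** SAP 7.1.3.1 takes "the last consecutive time point at which the difference is still statistically significant". SAP 5 takes "the first time point at which there is a non-significant difference between the two treatment groups" after a significant one. Both default to 12 h if no later non-significant time exists.

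SAP 4.1 describes SKAMP as an impairment scale on which 0 is normal, so benefit means d-ATS minus placebo below 0. The sample-size text (SAP 3.1, protocol 8.1) specifies a two-sided 0.05 level. The contrast in SAP 7.1.1 is labelled d-ATS minus placebo and has confidence limits, but no decision rule uses its sign.

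**The concern.** A two-sided p-value can fall below 0.05 in either direction. If a rule uses only the p-value, a time at which children are significantly worse on d-ATS passes the same test as one at which they are better.

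This matters most at the end of the day. Protocol 5.1 has the patch removed after 9 h, and SKAMP is rated again at 10 and 12 h. These ratings should show when the effect is lost. A significant reversal there would be the clearest sign that benefit had ended, yet it is not a non-significant difference, so under the written rule the effect continues.

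Onset and duration are the two secondary claims under type I error control. The window they define is also reused: SAP 7.1.3.1 repeats the primary analysis after dropping times before onset and after the end of efficacy. A window stretched by a reversal would carry into that sensitivity analysis.

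**Working it through.** **Step 1: reproduce the plan's own example.** The post-dose times are 1, 2, 3, 4.5, 6, 7, 9, 10 and 12 h. Under 7.1.3.1, onset is the first significant time, end is the last consecutive significant time, and duration is end minus onset. The SAP's example is significant from 1 to 10 h and not at 12 h: onset 1 h, end 10 h, duration 10 − 1 = 9 h. This matches the stated 9 h.

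**Step 2: apply the same rule when the sign reverses.** The patterns are hypothetical, with every listed difference significant.

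| Pattern | Literal 7.1.3.1 rule | With d-ATS minus placebo < 0 also required |
|---|---|---|
| A: better 1–10 h, worse at 12 h | 12 − 1 = 11 h | 10 − 1 = 9 h |
| B: better 1–9 h, worse at 10 and 12 h | 12 − 1 = 11 h | 9 − 1 = 8 h |
| C: worse at 1 h, better 2–10 h, not significant at 12 h | onset 1 h, duration 9 h | 1 h test fails; see objection |
| D: worse at all times | onset 1 h, duration 11 h | no onset |

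Pattern D also needs the gate to pass on a significantly worse day mean; the gate's wording allows this.

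These durations use the 7.1.3.1 end convention. SAP 5 puts the end at the first failed time instead. With the sign condition added, that gives 12 − 1 = 11 h for A (unchanged) and 10 − 1 = 9 h for B (down from 11 h).

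**Step 3: how often one time point would be significantly worse.** The SD and target difference are redacted, so the true worsening d is an assumption, in SDs of the within-child difference. With n = 74 completers, a paired test would give P = 1 − Φ(1.96 − d√74).

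The example code in SAP 7.1.1, reused for onset, has type=vc on subject by period and no subject effect. It therefore treats a child's two periods as independent. With between-period correlation ρ and equal variances at all times (both assumed), its standard error is too large by a factor 1/√(1 − ρ), so

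P = 1 − Φ(1.96/√(1 − ρ) − d√74).

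For ρ = 0.5 and d = 0.2: 1.96/0.707 = 2.77, 0.2 × 8.60 = 1.72, and 1 − Φ(1.05) ≈ 15%.

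| Assumed d | ρ = 0.3 | ρ = 0.5 | ρ = 0.7 |
|---|---|---|---|
| 0 | 1% | 0.3% | 0.02% |
| 0.1 | 7% | 3% | 0.3% |
| 0.2 | 27% | 15% | 3% |
| 0.33 | 69% | 53% | 23% |

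The last row assumes harm about as large as the benefit a paired design would detect with 80% power: (1.96 + 0.84)/√74 = 0.326.

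**Step 4: cost of the condition.** At a true benefit of 0.326, the paired chance of significance in the wrong direction is about one in a million. Power is 80.0% with or without the sign condition.

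**The case against.** The strongest reply is that direction is implied. The terms defined are onset and duration of efficacy, and asking whether a difference is still significant suggests the same difference persisting. SAP 7.1.3.1 also calls for LS-mean differences, confidence intervals and p-values at each time, plus a plot, so a reversal would be visible and an analyst would probably catch it. This stands as a reason to rate the problem low. It does not remove it: the rule as written gives the wrong answer, and correcting it would mean overriding a prespecified rule after unblinding. The plan can state direction where it wants to, as in the separate per-subject endpoint of a 50% reduction in SKAMP.

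Three stronger readings are tempting and not supported.

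- A reader might infer that a reversal is likely at 1 h or after patch removal. The documents give no data on this. A reversal of the whole-day mean is remote, because known amphetamine non-responders are excluded and only children who reached an optimal dose on d-ATS are randomised.
- A reader might use a paired test and report chances of about 13%, 40% and 80% at d = 0.1, 0.2 and 0.33. The SAP's example model is not paired, and its figures are lower whenever ρ is positive.
- A reader might say that a false onset at 1 h adds 1 to 2 h of duration. That presumes onset could otherwise be claimed at 2 or 3 h. SAP 7 stops testing once a hypothesis fails, and 7.1.3.1 states its duration rule only for significance at 1 h. On that reading, a failed 1 h test leaves no claim at all.

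**Conclusion.** The point holds on the text. The gate, onset and end rules in SAP 5, 7 and 7.1.3.1 and protocol 8.2.2 contain no sign condition. If a significant reversal occurred after patch removal, the 7.1.3.1 rule would overstate duration by 2 h (pattern A) or 3 h (pattern B) and shift the window used in the later sensitivity analysis. If one occurred at 1 h, it would be labelled onset and let testing proceed.

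The flaw has low probability. The size of any reversal and the between-period correlation are assumptions, and the percentages show only how the rule behaves under them. They do not predict this trial. The late-reversal durations depend on neither assumption; they need only the pattern to occur and the 7.1.3.1 end convention to be used.

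**What to change.** In SAP 5, 7 and 7.1.3.1 and protocol 8.2.2:

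1. Define success at the gate and at each time as meeting the stated p-value threshold on a two-sided test and an LS-mean difference, d-ATS minus placebo, below 0.
2. Treat the first time after onset at which this is not met, including a significant reversal, as loss of efficacy.
3. Report any significant difference against d-ATS as such.

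SAP 5 and 7.1.3.1 differ on whether the end is the first failed time or the last successful one, so the new clause should be written against a single agreed convention. The programmer should also confirm that the order of treatment levels makes the coded contrast d-ATS minus placebo.

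The cost is one clause in each place. It needs no new data or analysis and loses essentially no power.

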3.1 SAMPLE SIZE CONSIDERATIONS

Assuming a standard deviation (SD) of [REDACTED] and based on an average difference in total SKAMP scores between Placebo and d-ATS of [REDACTED], 74 subjects would need to complete the study to detect a true difference of [REDACTED] in mean total SKAMP scores between placebo and d-ATS at 80% power when testing at a significance level of $\alpha = 0.05$ (2-sided). Assuming a dropout rate of 20%, 90 subjects will be randomized and it is expected that 74 subjects will complete the study. A subject will be considered to have completed the study if the subject received both treatments during the double-blind Treatment Period and have completed both 12-hour classroom sessions during the double-blind Treatment Period.

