3.2 RANDOMIZATION

Randomization will occur prior to the start of the double-blind study period. Subjects will be randomized to one of the two treatment sequences (d-ATS then Placebo or Placebo then d-ATS) in a 1:1 ratio. Each eligible subject will be randomized to group assignment by a centralized Interactive Voice Response System (IVRS) /Interactive Web Response System (IWRS). Randomization will be applied centrally, without any stratification factors, across all sites to ensure even distribution of subjects across each treatment sequence.

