7. STATISTICAL METHODS

Summaries will be presented for the SP population for all subjects combined during the Dose-Optimization Period of the study. During the double-blind Treatment Period of the study, summaries will be presented for the FAS, Completers, and SP populations by treatment (i.e., d-ATS and placebo, with all d-ATS dose levels combined), and some tables by treatment and treatment sequence. Subjects are intended to receive both treatments during the double-blind cross-over period of the study, so summaries for Visits 6 and 7 will be combined, with subjects contributing data to both treatment columns for the combined time point. As a result, the numbers of subjects in each treatment arm in the header of these summaries will reflect the total number of subjects receiving the treatment, and the number of subjects contributing data for each visit will be presented in the body of the table.

Early termination visits will be mapped to the next scheduled visit for inclusion in summary tables, where appropriate. For example, a subject who terminates after Visit 3 (e.g., has assessments at Visits 1 - 3 and early termination assessments) would have assessments from early termination mapped to the next scheduled visit for each assessment. Different assessments may be mapped to different visits; in this example, most assessments would be mapped to Visit 4, ECG would be mapped to Visit 5 as no ECG assessments are scheduled to be performed at Visit 4. This mapping is considered part of the observed values, and will be conducted before any summaries or analyses are performed on observed values. Similarly, it will be conducted before any scoring algorithm is applied. Listings will present early termination data as the mapped visit, as well as under 'ET' Visit as well.

Unless otherwise noted, categorical variables will be summarized using counts and percentages. Percentages will be rounded to one decimal place, except 0% and 100% will be displayed without any decimal places. Continuous variables will be summarized using the number of observations (n), mean, standard deviation (SD), median, minimum, and maximum. All analyses will use SAS® version 9.1 or higher.

All raw data will be presented to the original number of decimal places. The means and medians will be presented to 1 more decimal place than the raw data. The standard deviations will be presented to 2 more decimal places than the raw data.

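### The log-rank comparisons of time to, and duration of, a 50% SKAMP reduction ignore that each child is in both arms, and the main duration analysis compares subsets selected after randomisation

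*SAP*

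**What the plan says.** SAP 3.2 sets up a two-sequence crossover: "Subjects will be randomized to one of the two treatment sequences (d-ATS then Placebo or Placebo then d-ATS) in a 1:1 ratio". SAP 7 confirms that tables pool the two visits, "with subjects contributing data to both treatment columns for the combined time point".

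SAP 7.1.3.1 has two approaches to onset and duration. The first uses the MMRM and feeds the closed testing procedure. The second is a survival analysis of a 50% fall in SKAMP total score from that day's pre-dose value. Its record is the classroom day: a child who never reaches the 50% fall "will be deemed to be censored at the last timepoint a SKAMP total score is recorded, for each classroom day". For the treatment comparison of onset times the SAP states: "The difference between treatment arms, d-ATS and placebo, will be assessed using the Log-Rank test". For duration: "Duration of effect will be analyzed using the same methodology as the onset of effect". No stratification by child, robust variance, frailty or period term is given for either.

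On children who never reach onset, the main duration rule is: "Subjects without an onset of effect will be excluded from the analysis of duration of effect". It then adds: "A sensitivity analysis will be performed where subjects without an onset of effect will be imputed to have duration of effect of 0 hours".

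**The concern.** There are two separate defects, with different consequences.

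**Pairing.** The ordinary log-rank variance assumes that the two samples are independent. Here they are the same children on two days. If a child who responds early on one day tends to do so on the other, the variance of the treatment contrast is smaller than the formula supposes. The p-value is then too large, and the efficiency of the crossover is lost. The SAP does recognise pairing and period elsewhere: SAP 7.1.3.5 plans McNemar, Mainland-Gart and Prescott tests for dichotomised CGI-I.

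**Selection.** Onset happens after randomisation and may well differ by treatment. Restricting duration to records with onset compares responders on d-ATS with a differently selected set of responders on placebo. A difference can then appear when no child's duration has changed, or a real one can be masked.

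Onset and duration are named secondary objectives, and these p-values would be reported as d-ATS versus placebo.

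**Working it through.** **The plan's own figure.** SAP 3.1 says "74 subjects would need to complete the study to detect a true difference of" a redacted amount, with 80% power at two-sided 0.05 for mean SKAMP. Solved backwards for 74 pairs, that implies difference/SD of within-child differences = (1.960 + 0.842)/√74 = 0.326. It cannot be reproduced forwards, because the SD and difference are redacted. No power, event count or hazard ratio is stated for the log-rank comparisons.

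**Inputs for onset.** From the documents: 74 children with two days each; scores at 1, 2, 3, 4.5, 6, 7, 9, 10 and 12 h; censoring after 12 h; alpha 0.05 two-sided. Assumed: exponential onset times on that grid, the onset proportions by 12 h, and a Gaussian-copula correlation between a child's two days.

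**Tests compared.**
- Ordinary log-rank: z = U/√V, with U = Σ(d₁ − d·p) and V = Σ d·p(1 − p)(n − d)/(n − 1). Here p is the share of those at risk who are on d-ATS.
- Child-clustered: add the score contributions of each child's two days to give cᵢ; z = Σcᵢ/√Σcᵢ².
- Log-rank stratified by child.

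**Results for onset**, 5,000 runs per setting (Monte Carlo SE about 0.3 points at 5%, 0.7 points at 50%):

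| Correlation | 0 | 0.3 | 0.5 | 0.7 |
|---|---|---|---|---|
| Level, 50% vs 50%: ordinary | 5.5% | 2.4% | 1.3% | 0.5% |
| Level: clustered | 5.3% | 4.6% | 4.8% | 4.7% |
| Level: stratified by child | 5.4% | 4.6% | 5.1% | 5.2% |
| Power, 50% vs 35%: ordinary | 47% | 46% | 45% | 45% |
| Power: clustered | 46% | 55% | 63% | 77% |
| Power: stratified by child | 37% | 42% | 49% | 65% |

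Cross-check: the variance of the ordinary z under the null was 0.764 at correlation 0.3 and 0.613 at 0.5. Then 2[1 − Φ(1.96/√0.764)] = 2[1 − Φ(2.24)] = 2.5%, and 2[1 − Φ(1.96/√0.613)] = 2[1 − Φ(2.50)] = 1.2%, which agree with the simulated levels. Repeat runs gave levels of 2.2–3.2%, 1.2–1.7% and 0.2–0.5% at the three positive correlations.

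**Power lost against the clustered test** at correlation 0.3 / 0.5 / 0.7:
- 50% vs 35%: 54.7 − 45.8 = 9, 63.2 − 45.3 = 18 and 76.9 − 44.9 = 32 points; about 9 to 33 across repeats.
- 60% vs 35% (2,000 runs): 92/93/96% ordinary against 95/97/100% clustered, a loss of about 3 to 5 points allowing for rounding.
- 60% vs 30% (2,000 runs): 98/99/99.5% against 99/100/100%, about 1 point or less.
- 60% vs 20% and 70% vs 30%: no loss.

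**Duration**, 2,000 runs per setting, with no treatment effect on duration in any child, onset correlation 0.5, and only the day without onset dropped (the SAP does not say whether a child with onset on one day loses that day or both). Ordinary log-rank rejections:

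| Onset, d-ATS / placebo | Onset-only, duration unrelated to tendency to respond | Onset-only, duration linked to it | Zero-hours, unrelated / linked |
|---|---|---|---|
| 30% / 30% | 6.0% | 4.3% | 2.9% / 1.5% |
| 50% / 20% | 5.3% | 8.9% | 83% / 71% |
| 60% / 20% | 4.7% | 13.0% | 97% / 92% |
| 70% / 30% | 5.3% | 13.8% | 94% / 81% |

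The onset-only rejections rise only when onset shares differ and duration is linked to the tendency to respond. In these settings the mean z was 0.7 to 1.0 in the direction that makes duration on d-ATS look shorter. Other dependence could push it the other way. Only about 16% to 27% of children contributed to both arms. The zero-hours analysis rejects often at unequal onset shares because it is also testing onset.

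**The case against.** The strongest reply is that little hangs on these tests. The survival approach comes second in SAP 7.1.3.1. The closed procedure in SAP 7 and Protocol 8.2.2 runs on MMRM p-values, and Protocol 8.2.2 contains no 50%-reduction analysis. That stands. A reader might infer that the ordered onset and duration claims, or the primary result, are compromised; the documents do not support this.

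A reader might also take a miscalibrated p-value to mean a risk of falsely claiming onset. With positive within-child correlation the level is below 5%, so the harm from ignoring pairing is a missed effect.

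The power loss is fairly attacked too. It depends on a correlation and onset rates that the documents do not give, and it nearly vanishes for large contrasts. Only children who reached an optimal dose are randomised (SAP 3), so large contrasts are plausible. Onset is judged against the same day's pre-dose score, so a high correlation between days cannot be presumed. This limits the size of the point, but it does not justify the test: clustering costs about 1 point of power at most at correlation 0.

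Finally, the SAP already plans a zero-hours sensitivity analysis, which brings back the excluded children. It is tempting to make that the main duration analysis. But it uses the same unpaired test, and it rejected in 71% to 97% of runs with unequal onset and no duration effect. It answers a question about onset and duration combined. Duration among responders remains a legitimate descriptive question.

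**Conclusion.** The point holds as a correction to supportive analyses. The test named for onset is wrong for paired data and conservative under positive within-child correlation. The lost power ranges from substantial at a modest contrast to negligible at a large one, and is nil at correlation 0. The loss of 9 to 33 points belongs to one assumed contrast and should not be read as the expected loss in this trial.

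The main duration comparison is between groups formed after randomisation. It can mislead in either direction when onset rates differ by treatment and duration is linked to the tendency to respond; otherwise its level stayed near 5%. The direction of the pairing error and the selection problem follow from the design. Every magnitude here rests on assumed correlations, onset rates and a duration model.

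**What to change.** In SAP 7.1.3.1, keep the Kaplan-Meier plots and quartiles. Replace the log-rank p-value with a Cox model or log-rank score that uses robust variance clustered on child, with period as a covariate. Apply this to onset and to any p-value given for duration, including the zero-hours analysis. In SAS this is PHREG with COVS(AGGREGATE) and the child as ID. A log-rank stratified by child would also hold the level, but at correlation 0.3 it had less power than even the ordinary test (42% against 46%).

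Label the onset-only duration comparison descriptive and not a randomised comparison, and state whether a child with onset on one day only loses that day or both. Label the zero-hours analysis a composite of onset and duration. State that these results sit outside the closed test.

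The cost is a few lines of code and some SAP wording. SAP 1 already provides for a final SAP2 before database lock. No extra data or children are needed.
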